10.2.2 Secondary

The same statistical method and model as above is used for the other secondary outcome measures where there are more than two measurement points

In addition to analyzing total scores as continuous variables, we will also do descriptive analyses of treatment response and remission status. For this purpose, we use established cut-offs. Response according to the SHAPS is defined as an improvement of  $\geq 50\%$  on total score (each item rated from 1-4), and remission as a SHAPS score of  $\leq 2$ , based on an alternative scoring approach in which each item is rated either 0 or 1 (10, 11). Initially, the published protocol defined SHAPS remission as a score of  $\leq 3$ . However, to maintain consistency with the original Snaith et al. publication (12) — the basis of our SHAPS inclusion criteria — we've updated the definition to a score of  $\leq 2$ . This was done before all data had been collected and before the randomization code was broken.

Response on the MADRS is defined as ≥50% improvement and remission as a score ≤10. Fisher's Exact test will be used to compare dichotomous outcomes.

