## 6.2 Sample size calculation

For the primary question (SHAPS), a linear mixed model with repeated measures (w 3, w 6 and w 9) will be used, where the primary question will be answered with the overall comparison between the

randomized groups. Any group differences at baseline are corrected by including the baseline values as a covariate in the model. The estimated effect size of pramipexole treatment is estimated at 0.27 as this has been reported in other studies of antidepressant drugs. This corresponds to a score difference in MADRS of approximately 4 points which is considered a clear clinical improvement and corresponds to  $\geq$  4 points on SHAPS. Estimate of the correlation coefficient between repeated measures of MADRS scores is based on material from our previous pilot study (r=0.5). In a power calculation with strength of 80% and  $\alpha$ =0.05, 74 research subjects were estimated to be needed. In the original power calculation, the number of dropouts was estimated to be less than 5% (based on the pilot study), whereby we needed to include 80 research subjects in the study (ITT)

After a planned interim analysis, conducted by an external statistician, we estimate that we need to include 80 patients who reach the week 9 visit (end of study).

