#### 6.4 Interim analysis

An interim analysis was planned according to the original protocol. In June of 2024 an independent statistician conducted an interim analysis on the primary outcome and number of dropouts. The result of this interim analysis was that we decided to increase the number of recruited patients to 80 with complete efficacy data through the week 9 visit.

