### 8 Outcome measures

### 8.1 Primary efficacy outcome measures

The primary efficacy outcome measure is the absolute change in the SHAPS (2) between baseline and week 9.

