### 8.4 Safety outcome measure

#### Adverse events

# 9 Data processing

### 9.1 Missing values

If clinical efficacy measurement values are missing at different times, this will be compensated for with last-observation-carried-forward (LOCF).

For the mechanistic secondary outcomes (e.g. fMRI), analyses will be performed only on those subjects who have the necessary data available for these specific analyses, meaning that no imputation will be applied.

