### 10.2 Effect

### 10.2.1 Primary

To answer the primary question, a linear mixed model with repeated measures is used with severity of anhedonia symptoms (SHAPS total score) as the dependent variable and time (week), treatment (pramipexole or placebo), and the interaction of time by treatment as independent variables. The

SHAPS total score at baseline will be used as a covariate in the model. In the event of missing measurements at different time points, this will be compensated for with last observation carried forward (LOCF). Normal distribution is expected based on previous studies.

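### Response and remission inherit the general last-observation-carried-forward rule and name no visit, so an early improver who then withdraws counts as a success in Fisher's exact test

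*SAP*

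**What the plan says.** Section 10.2.2 introduces the binary outcomes as an addition to the continuous scores: "we will also do descriptive analyses of treatment response and remission status". For the first scale it states "Response according to the SHAPS is defined as an improvement of" at least 50%, and it sets a remission cut-off on the alternative 0/1 item scoring. For the second scale, and for the test, it says: "Response on the MADRS is defined as ≥50% improvement and remission as a score ≤10. Fisher's Exact test will be used to compare dichotomous outcomes". The section does not say at which visit status is determined, or how a patient who has left the trial is classified.

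The general rule on missing data is in section 9.1: "If clinical efficacy measurement values are missing at different times, this will be compensated for with last-observation-carried-forward (LOCF". The only exception there is for mechanistic outcomes such as fMRI, which are analysed without imputation. Section 10.2.1 repeats LOCF for the primary model.

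Week 9 as the endpoint is stated for the primary outcome in section 8.1: "The primary efficacy outcome measure is the absolute change in the SHAPS (2) between baseline and week 9". The post-baseline visits appear in section 6.2: "a linear mixed model with repeated measures (w 3, w 6 and w 9) will be used".

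**The concern.** Response and remission are calculated from the clinical scores that section 9.1 fills in. Once a week 3 or week 6 score has been carried to week 9, the status derived from it is carried too. Someone who crossed a cut-off early and then stopped attending, for whatever reason, enters the two-by-two table as a success although no end-of-trial outcome was observed.

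This differs from the question of LOCF in the mixed model. If the model were changed to use observed scores only, the Fisher tests would still follow section 9.1. The binary outcomes therefore need a sentence of their own.

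At stake is the between-arm comparison of response and remission. It is tested at the two-sided 0.05 level without multiplicity adjustment (section 10.1), and such rates are easily quoted. The arm that loses more patients after early improvement gains successes that were not seen at week 9.

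**Working it through.** **What the rule does, by time of withdrawal** (visits from section 6.2, rule from section 9.1)

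- Leaves before week 3: only the baseline score exists. Carried forward, it shows no improvement, so the patient is a non-responder.
- Leaves after week 3 or week 6 without meeting a cut-off: non-responder.
- Leaves after week 3 or week 6 having met a cut-off at the last observed visit: responder or remitter.

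Only the third group is affected.

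**The plan's own figures.** The SAP gives no response rate and no dropout by arm, so there is no stated figure on this point to reproduce. The sample size belongs to the continuous primary outcome and is not in dispute. Reading 0.27 as Cohen's f, with 3 visits and r=0.5, the noncentrality is 0.27² × 74 × 3 / (1 + 2 × 0.5) = 8.09 on 1 and 72 degrees of freedom. This gives power 0.801 at N=74. Allowing 5% dropout, 74 / 0.95 = 77.9, or 78, which is within the planned 80.

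**Illustration 1.** All counts are assumptions. Sections 6.2 and 6.4 set 80 patients reaching week 9. With an assumed 9% dropout, 80 / 0.91 = 87.9, or 88 randomised, which is 44 per arm under an assumed equal allocation. One patient is then 1/44 = 2.3 percentage points. Start from 12 active and 5 placebo responders observed at week 9 (two-sided Fisher's exact test):

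| Carried-forward responders (active, placebo) | Table | Difference | p |
|---|---|---|---|
| 0, 0 (withdrawals count as failures) | 12/44 v 5/44 | 15.9 points | 0.103 |
| 1, 0 | 13/44 v 5/44 | 18.2 points | 0.062 |
| 2, 0 | 14/44 v 5/44 | 20.5 points | 0.036 |
| 3, 0 | 15/44 v 5/44 | 22.7 points | 0.021 |
| 2, 1 | 14/44 v 6/44 | 18.2 points | 0.073 |

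**Illustration 2.** This also rests on assumptions: 40 completers per arm, with 14 v 6 responders among them, and four dropout patterns (active/placebo).

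| Dropouts | p, none carried | p, one active carried | p, two active carried |
|---|---|---|---|
| 2/2 | 0.071 | 0.042 | 0.024 |
| 4/2 | 0.074 | 0.045 | 0.026 |
| 6/2 | 0.081 | 0.0498 | 0.030 |
| 8/4 | 0.082 | 0.051 | 0.031 |

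Both sets show that one to three patients can matter at this trial size. Neither predicts what happened in the trial. The last row of the first table shows that roughly balanced carry-forward leaves p above 0.05.

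**The case against.** **A rule already exists.** Section 9.1 covers all clinical efficacy values, so missing data are not left unaddressed. This stands. The point is that a pre-specified rule suits these outcomes badly. There is no gap or contradiction in the handling of withdrawals, although the assessment visit is not named.

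**The outcomes rank low.** They are called descriptive and are absent from the list in section 8.2, and no confirmatory claim rests on them. This stands and limits the weight of the point. It does not remove it, because the same section prescribes a test between arms.

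**The illustrations are one-sided and chosen near 0.05.** This stands. The only dropout figure in the SAP is the original assumption of below 5%. At 5%, 80 / 0.95 = 84.2, so there would be only four or five dropouts in total, and three carried-forward active-arm responders would be most of them.

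**SHAPS response is hard to reach early.** A maximum of 56 with items scored 1 to 4 means 14 items and a floor of 14. A 50% fall in the total is impossible from a baseline below 28, and from 40 it needs a score of 20 or less. This narrows the scenario for SHAPS response. It does not apply to SHAPS remission, which uses a different scoring, or to MADRS.

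**Counting withdrawals as failures is also single imputation.** This is true, and it is why LOCF and observed-case tables should stand beside it.

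A reader might infer that the pramipexole arm will be favoured through withdrawals for poor tolerability. The SAP does not support that. It gives no dropout by arm and no reasons for leaving. On the interim analysis, section 6.4 says only: "In June of 2024 an independent statistician conducted an interim analysis on the primary outcome and number of dropouts".

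**Conclusion.** The point holds as a weakness in the analysis of secondary outcomes that are called descriptive but are tested. As written, the plan counts a patient who met a cut-off at week 3 or 6 and then withdrew as a success. The comparison is biased if such withdrawals differ between arms. The primary result is not affected.

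That week 9 is the intended visit for these outcomes is an inference from the nine-week treatment period (section 6.1) and the primary outcome (section 8.1). Size and direction cannot be derived from the SAP. Under the assumed 44 per arm, the shift is 2.3 points per carried-forward patient. Whether p crosses 0.05 depends entirely on assumed counts: it does with two or three carried forward in the active arm only, and does not with one, or with two active and one placebo.

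Two stronger readings should be avoided: that the SAP has no rule for withdrawn patients, and that the reported response comparison will be falsely significant. Section 9.1 rules out the first, and nothing in the SAP establishes the second.

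**What to change.** Add to section 10.2.2: *Response and remission are assessed at week 9. All randomised patients remain in the denominator. A patient without an observed week 9 score is counted as not responding and not in remission; the carry-forward rule in section 9.1 does not apply to these outcomes in the main table.* Present the LOCF and observed-case versions as sensitivity tables, and report by arm how many patients lack a week 9 score and how many of them had met a cut-off at their last visit.

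The cost is a few sentences, one recoded variable and two extra tables, with no new data. The downside should be stated in the plan: rates become lower, more so in the arm with more missing week 9 visits, and a patient who merely missed that visit is counted as a failure. The sensitivity tables show how far the result depends on this choice.

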#### 6.3 Randomization

The randomization process uses a randomization list generated by an independent statistician at Clinical Studies Sweden – Forum South. Blinded study personnel are unaware of the randomization outcome. Research participants are included/randomized consecutively as they are deemed eligible for the study.

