# 10 Statistical analysis

#### 10.1 Statistical basis

Descriptive statistics will be given as mean (SD), median (Q1–Q3) and (Min–Max) for continuous variables. The number of observations will also be given.

The randomization groups will be compared. Two-sided test of statistical significance is to be used, and the chosen significance level is 0.05. No adjustment for multiplicity will be made.

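### Cheap improvement: response and remission are compared only by an unadjusted Fisher's exact test, which is valid but runs at about 3% or less at 40 per arm and leaves out the baseline score

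*SAP*

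**What the plan says.** Section 10.2.2 adds response and remission to the total-score analyses: "we will also do descriptive analyses of treatment response and remission status". Response is an improvement of at least 50% on SHAPS or MADRS. Remission is an absolute cut-off: 2 or less on SHAPS under 0/1 item scoring, and 10 or less on MADRS. The only comparison named for these four outcomes is Fisher's "Exact test will be used to compare dichotomous outcomes". No covariate, effect estimate or confidence interval is given for them.

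Section 10.1 sets the general rule: "Two-sided test of statistical significance is to be used, and the chosen significance level is 0.05". It continues: "No adjustment for multiplicity will be made".

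The continuous analyses are treated differently. Section 6.2 says: "Any group differences at baseline are corrected by including the baseline values as a covariate in the model". Section 10.2.1 puts this into the primary model: "SHAPS total score at baseline will be used as a covariate in the model". Section 10.2.2 carries that model to secondary scales with more than two measurement points.

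On numbers, section 6.2 says that after the interim analysis "we estimate that we need to include 80 patients who reach the week 9 visit". The SAP gives no event rates or power for the dichotomous outcomes and no allocation ratio.

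**The concern.** Two features cost efficiency.

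- Fisher's test conditions on the total number of events. With about 40 per arm the attainable p-values are coarse, so the true error rate falls well short of the nominal 5%, most of all when events are few.
- The test cannot use the baseline score, which the plan uses for the continuous analyses. Remission is an absolute cut-off, so a patient's chance of reaching it depends on where that patient started.

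At stake is some power for four supporting comparisons. A real difference in remission could be reported as non-significant next to a baseline-adjusted result on the same scale that points the other way. A Fisher p-value alone also gives no estimate of the difference in proportions, which is what a descriptive analysis most needs.

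**Working it through.** **The plan's own figure.** Section 6.2 gives 74 subjects for the primary outcome (effect size 0.27, r = 0.5, three visits, 80% power, two-sided 0.05). Reading 0.27 as Cohen's f, λ = f²·N·m / (1 + (m−1)r) = 0.27² × 74 × 3 / (1 + 2 × 0.5) = 8.09. On an F test with 1 and 72 degrees of freedom this gives power 0.801, so 74 reproduces. Then 74 / 0.95 = 77.9, which 80 covers. None of this concerns the dichotomous outcomes, for which there is no stated figure to reproduce.

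**Inputs for the check.**
- 40 per arm: 80 patients from section 6.2, with 1:1 allocation assumed.
- Two-sided 0.05: section 10.1.
- Event rates: assumed. The 33% echoes the roughly one third of pilot patients in section 4 who showed an effect, but that effect is not defined there as response or remission. The comparison rates are free assumptions.
- Baseline to week 9 correlation: assumed 0, 0.3 or 0.5. The 0.5 in section 6.2 is for repeated MADRS scores in the pilot.

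**Step 1: size of Fisher's test.** Enumerate all 41 × 41 outcomes at 40 vs 40 and add the binomial probabilities of those with Fisher p < 0.05, at a common event rate:

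| Event rate | 5% | 10% | 15% | 50% | Maximum |
|---|---|---|---|---|---|
| True size | 0.4% | 1.7% | 2.5% | 3.3% | 3.3% |

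This result needs no correlation assumption.

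**Step 2: an exact test that spends more of the 5%.** Boschloo's test uses the Fisher p-value as its statistic and calibrates it over all null rates. At 40 vs 40 this means rejecting at Fisher p ≤ 0.0707, with maximum size 4.8%. It rejects whenever Fisher's test does.

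**Step 3: power, and the gain from baseline.** Powers of the two exact tests are enumerated. The last three columns are points gained over Fisher's test within the same simulated trials (10,000 per setting). Baseline is standard normal, the week 9 value is correlated with it at r and cut at an absolute threshold. The test is a logistic score test adjusted for baseline, with a switch to Boschloo's test if fewer than 10 patients in total meet the definition.

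| Rates | Fisher | Boschloo | Gain, r = 0 | Gain, r = 0.3 | Gain, r = 0.5 |
|---|---|---|---|---|---|
| 33% vs 10% | 64.8% | 70.2% | 8.6 | 10.2 | 14.0 |
| 33% vs 15% | 38.5% | 44.6% | 9.7 | 11.5 | 15.6 |
| 20% vs 5% | 41.1% | 48.4% | 11.5 | 12.2 | 14.0 |

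Boschloo's gains are 70.2 − 64.8 = 5.4, 44.6 − 38.5 = 6.1 and 48.4 − 41.1 = 7.3 points. Taking one third exactly in place of 33% moves the exact powers in the first two rows up by about a point (66% to 71%, 40% to 46%). A separate run at r = 0.5 then gave 66% to 79% for the first row, so the low end there is about 13.

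The switch matters for 20% vs 5%. The expected total is 40 × 0.20 + 40 × 0.05 = 10, and the probability of fewer than 10 is 45%. Without the switch the gain at r = 0.5 would be 18 to 20 points; with it, about 14.

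**Step 4: response.** Response means Y ≤ 0.5B, where B is baseline and Y is week 9. The underlying variable is L = Y − 0.5B, with cov(L, B) = r·sd(Y)·sd(B) − 0.5·sd(B)². With equal SDs and r = 0.5 this is zero. With sd(Y)/sd(B) = 1.5 the correlation is (0.75 − 0.5)/√(2.25 + 0.25 − 0.75) = 0.19. Simulated gains of adjusted logistic regression (likelihood-ratio test, no sparse-count switch) over Fisher's test, for rates of 33% vs 10%, 40% vs 15%, 45% vs 20%, 50% vs 20% and 60% vs 30%, are 6 to 10 points at correlation 0 and 7 to 13 at 0.19 to 0.3. Most of this is Fisher's conservatism.

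One caveat applies. Section 9.2 scores SHAPS items 1 to 4 with a maximum of 56, so there are 56/4 = 14 items and a floor of 14. Halving the total is impossible from a baseline below 28. The model has no floor and may understate how far SHAPS response depends on baseline.

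**Step 5: price of adjustment.** The simulated null size of the adjusted score test is about 4% to 6%, against a guaranteed ceiling of 5% for either exact test.

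**The case against.** The case for leaving the plan alone is substantial. Fisher's test is conventional and controls the error rate. The SAP calls these analyses descriptive, the sample size does not rest on them, and a baseline-adjusted analysis of SHAPS total score is already planned. With no multiplicity adjustment, a conservative test on four supporting outcomes does no harm to error control. The replacement is asymptotic, and part of its gain comes simply from operating closer to 5%. All of this stands, and it makes the point optional in weight.

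It does not remove the point. Section 10.2.2 calls the analyses descriptive and then prescribes a significance test, to which section 10.1 attaches a 0.05 threshold. If they are descriptive, a difference with an interval is wanted and none is specified. If they are tests, a uniformly no-less-powerful exact test is available.

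Three stronger readings are tempting, and the document supports none of them:
- A reader might infer that all four comparisons lose 13 to 18 points of power. That range needs an absolute cut-off and a correlation near 0.5, which the SAP gives neither for baseline versus week 9 nor for SHAPS. Its upper end also disappears once sparse counts go to Boschloo's test.
- A reader might infer that the SAP misstates its significance level. For an exact test 0.05 is a ceiling, and Fisher's test respects it. Boschloo's test also falls below it, to about 3% at a 10% event rate.
- A reader might infer that chance baseline imbalance biases the comparison. Under randomisation the unadjusted test's error rate already allows for it; the loss is one of precision.

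**Conclusion.** The point holds as a low-cost improvement; nothing in section 10.2.2 is invalid. The firmest part is the conservatism: at 40 per arm, Fisher's test has true size of at most 3.3%, and below 2% at event rates of 10% or less. This rests only on the arm sizes, and so on the assumed 1:1 allocation.

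The power figures depend on assumed event rates. Boschloo's test returns about 5 to 7 points. Baseline adjustment returns in total about 13 to 16 points for remission at r about 0.5, about 9 to 12 at r from 0 to 0.3, and about 6 to 13 for response, where baseline is already in the definition. The primary analysis and its sample size are untouched.

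**What to change.** In section 10.2.2, replace the Fisher sentence with wording to this effect: each response and remission outcome is compared between arms by logistic regression (score test) with treatment and the baseline total score of the same scale, reporting the baseline-standardised difference in proportions with its 95% CI; if fewer than 10 patients in total meet a definition, Boschloo's unconditional exact test is used instead.

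If an exact test is preferred throughout, the minimum change is to replace Fisher's test with Boschloo's and report the difference in proportions with its 95% CI. This keeps the 5% ceiling but leaves the baseline score unused.

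The cost is one sentence in the SAP and a few lines of code in software already listed in section 11, with no new data or patients. The downside of the adjusted test is its asymptotic size of about 4% to 6%; Boschloo's test avoids that but gains less power.

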10.3 Additional

fMRI experimental designs and planned analysis as well as accelerometry analysis are described in the Protocol (1).

10.4 Safety

Adverse events will be presented within randomization groups.

# 11 Statistical program

IBM SPSS Statistics 28 or higher Windows (IBM Corporation, Armonk, NY, USA), SAS Enterprise Guide 8.3 for Windows (SAS Institute Inc., Cary, NC, USA) or R will be used for the statistical analyses. A p-value below 0.05 was considered significant.

